An inter-regional connectivity mapping using an extended time-series (typically 200-400 whole-brain volumes acquired over 8-15 minutes) of BOLD fMRI images acquired in an unstimulated state will be utilized for Aim 3. Resting-state connectivity analyses will be used to better characterize tinnitus-related network abnormalities using Independent Components Analysis, using analysis of variance (ANOVA) comparing Baseline versus Posttreatment factors, while regressing out demographic variables. The mid-treatment scan will be used to infer causal effects of Cognitive Processing Therapy by demonstrating the temporal changes in resting-state networks.

Missing data. If missing data can be assumed to be missing at random, likelihood-based mixed model analysis will provide valid inferences using data from all cases with any outcome data. The impact of attrition on analyses will be addressed by comparing those who are available for analysis at each assessment with those who are not using appropriate data from prior assessments.

6.7 Confidentiality. All in-person therapy sessions and interview assessments will be delivered in private offices at the STRONG STAR Clinic at the UTHSCSA. Data will be stored by an assigned participant code number. Digital audio recordings of assessments and CPT sessions will be labeled with the participant's study id number and uploaded onto the secure STRONG STAR server. Encrypted email will be used to securely send recordings to research experts who are part of the research team for review of fidelity. Every member of the Research Team will be trained and monitored about how to handle and protect both medical and research records. Furthermore, the Research Team strictly controls access to study data.

6.7.1 Certificate of Confidentiality.

We are not seeking a Certificate of Confidentiality.

6.7.2. Data Protection. Data will be coded using an assigned number. Assessments and data collected during the treatment sessions will be stored in a locked cabinet at the STRONG STAR Clinic at the UTHSCSA. Digital audio recordings of assessments and CPT sessions will be labeled with the participant's study id number and uploaded onto the secure STRONG STAR server. All UTHSCSA STRONG STAR network connectivity is segmented with Access Control Lists and is not accessible to any other UTHSCSA network segments. STRONG STAR data server is physically located at the Advanced Data Center (ADC) has 24x7 onsite security, card key, biometric access controls and video surveillance. University of Texas Health Science Center at San Antonio (UTHSCSA) ADC facility also maintains Gen 2 firewall devices to protect and prohibit any unauthorized access to UTHSCSA data. All UTHSCSA network devices are monitored by state of the art monitoring applications that include configuration audit, management, and availability 24x7.

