113 reductions in both PTSD symptoms and tinnitus-related distress at a one-month follow-up assessment. This study
114 will be the first to demonstrate the importance of addressing PTSD in order to target tinnitus-related distress.
- 115 ▪ After one month of completing CPT for individuals with both PTSD and tinnitus, a decrease in neurobiological
116 connectivity will be demonstrated between the attention network and limbic network, demonstrating the role of
117 cognitive control in reducing psychological distress.

118 **4. BACKGROUND AND SIGNIFICANCE.**

119 **Tinnitus and PTSD**

120 The genesis of tinnitus and PTSD can both be potentially associated to the same psychological and acoustic traumatic
121 event while deployed, with clinical implications concerning the recovery of both auditory and psychological disorders.
122 Tinnitus can be conceptualized as one such conditioned stimulus, continuing to serve as a reminder of the traumatic event
123 (Criterion B of PTSD). In a study of Cambodian refugees, significantly more participants with PTSD had tinnitus compared
124 to participants without tinnitus (Hinton, Chhean, Pich, Hofmann, & Barlow, 2006). Tinnitus patients were significantly more
125 likely to have PTSD compared to participants without tinnitus. In the same study, most participants with tinnitus indicated
126 experiencing flashbacks and an overwhelming 91.7% of those flashbacks accompanied tinnitus. Second, symptoms of
127 avoidance (Criterion C of PTSD) are also demonstrated among individuals with tinnitus. Fagelson (2007) found similarities
128 in avoidant symptoms between veterans with both tinnitus and PTSD; and those with only tinnitus. Individuals in both
129 groups reported similar aversions to loud warning signals and a reduction in tolerance to loud noises. Andersson and
130 Westin (2008) explain that individuals may choose to avoid noise and seek quieter places. Third, negative alterations in
131 mood and cognition (Criterion D of PTSD) are observed among individuals with tinnitus. Tinnitus-associated trauma recall
132 and catastrophic cognitions significantly predicted PTSD severity, while controlling for tinnitus severity, among Cambodian
133 refugees suffering from both tinnitus and PTSD (Hinton et al., 2006). Fourth, individuals with tinnitus demonstrate
134 emotional reactions that overlap with hypervigilance or hyperarousal (Criterion E of PTSD). Fagelson and Smith (2016)

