The recruited sample size will be 30 participants. Based on work by Salinas and Szabo (2017), 10 participants will provide adequate power to detect differences in resting-state networks, from pre-, mid- and to posttreatment fMRI scans. In their

428 paper, they examined 14 baboons, pre- and posttreatment injection of valproic acid, at three different time points, with
 429 adequate power.
 430

Estimate Required Sample Size	10
Estimate Participant Screen Out	18 (~60%)
Estimate Participant Withdrawal	2 (~7%)
Total Enrollment Requirement	30

431
 432
 433
434 6.4.2 Primary (i.e., primary outcome variables) and secondary endpoints.
 435

436 Primary outcomes include changes in scores on measures of PTSD (CAPS-5 and PCL-5) and tinnitus-related distress (TFI
 437 and TAQ). The additional primary outcome is changes in functional activity within resting-state networks, provided by fMRI
 438 scans.
 439

440 Secondary outcome variables include changes in scores on measures of depression and suicide (DSSI-SS; PHQ-9), anxiety
 441 (GAD-7), sleep impairment (PROMIS; ISS; STOP), general health and functioning (VR-12; BIPF), and alcohol and substance
 442 use (FTND; FTND-ST; AUDIT).
 443
 444
 445
 446

447 **6.4.3 Hypotheses and Specific Data Analysis Plans.**
 448

449 Hypothesis 1: There will be significant overlap between tinnitus distress and PTSD symptoms, as measured by the
 450 Clinician Administered PTSD Scale for DSM-5 (CAPS-5), the PTSD Checklist for DSM-5 (PCL-5), the Tinnitus Functional
 451 Index (TFI), and Tinnitus Acceptance Questionnaire (TAQ). Findings will help clinicians' understanding of the distinct ways
 452 in which each disorder contributes to functional impairment. Results will substantially improve clinicians' ability to
 453 conceptualize patients with comorbid tinnitus and PTSD.
 454

455 Analysis plan: Non-inferential statistics will be calculated to include central tendencies, standard deviations, and
 456 alpha coefficients. Unusual distributions, missing data, or outliers will be identified. PTSD symptom cluster
 457 severity (intrusions, avoidance, negative alterations in mood and cognition, and hyperarousal) will be calculated
 458 using the data gathered from the CAPS-5. Tinnitus domains of distress will be calculated using the data gathered
 459 from the Tinnitus Functional Index. Pearson product-moment correlation coefficient analyses will be used to
 460 examine the overlap between tinnitus and PTSD.

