461 Hypothesis 2: There will be similar neurological activity associated with PTSD and tinnitus as measured by resting state
 462 fMRI. Down-regulation and up-regulation of neurobiological connectivity of the networks will be examined within the
 463 auditory, limbic, default-mode, and attentional networks. Results will provide insight concerning the neurological
 464 maintenance factors for both disorders. Study findings will be utilized to generate new and innovative therapeutic
 465 approaches that target specific brain regions to alleviate tinnitus and PTSD.
 466

467 Analysis plan: An inter-regional connectivity mapping using an extended time-series (typically 200-400 whole-
 468 brain volumes acquired over 8-15 minutes) of BOLD fMRI images acquired in an unstimulated state (Biswal et al.,
 469 1995; Xiong et al., 1999) will be utilized for Aim 2. Inter-connected regions show temporally correlated variations,
 470 allowing connectivity to be detected and quantified. Resting-state networks (RSNs) have been used to map
 471 scores of functional systems. They are now viewed as reflecting the intrinsic architecture of the brain (Smith et al.
 472 2009). Resting-state connectivity analysis of the auditory system in normal subjects demonstrated highly coherent
 473 within-system connectivity, as well as strong projections to the frontal limbic circuitry (Hunter et al., 2006).
 474 Resting-state connectivity analyses will be used to characterize tinnitus-related network abnormalities.
 475

Hypothesis 3:

- Individuals with tinnitus and PTSD who received Cognitive Processing Therapy will demonstrate significant reductions in both PTSD symptoms and tinnitus-related distress at a one-month follow-up assessment, AND
- After one month of completing CPT for individuals with both PTSD and tinnitus, a decrease in neurobiological connectivity will be demonstrated between the attention network and limbic network, demonstrating the role of cognitive control in reducing psychological distress.

Analysis plan: Post-treatment outcome data will be compared to participants' baseline measures of tinnitus-related distress and PTSD. Data will be analyzed using a general linear mixed (GLM) model with baseline scores of tinnitus-related distress used as a covariate. The analyses will demonstrate whether individuals who received CPT experienced a reduction in tinnitus-related distress and PTSD symptoms.

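### The mid-treatment scan is given a causal role that a one-intervention design cannot support and is left out of the only stated imaging test; the rank of the Hypothesis 3 imaging test is also undeclared

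*Combined protocol and SAP*

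**What the plan says.** **Scans and design.** Section 5 and the Section 6.2 table schedule three resting-state scans: baseline, mid-treatment (after Session 6 and before Session 7 of CPT) and one month after treatment. Section 5 describes a single intervention level, CPT, given to everyone.

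**Sample size.** Section 6.4.1 says that 10 participants give "adequate power to detect differences in resting-state networks, from pre-, mid- and to posttreatment fMRI scans".

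**Imaging test.** Under Hypothesis 3, Section 6.4.3 applies Independent Components Analysis, "using analysis of variance (ANOVA) comparing Baseline versus Posttreatment factors", with demographic variables regressed out. The next sentence covers the remaining scan: "The mid-treatment scan will be used to infer causal effects of Cognitive Processing Therapy by demonstrating the temporal changes in resting-state networks".

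**Primary imaging outcome.** Section 6.4.2: "The additional primary outcome is changes in functional activity within resting-state networks". No network, measure or time point is named.

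**Imaging predictions.** Hypothesis 3 (Sections 3 and 6.4.3) expects that one month after CPT "a decrease in neurobiological connectivity will be demonstrated between the attention network and limbic network". Hypothesis 2 uses other wording: "Down-regulation and up-regulation of neurobiological connectivity of the networks will be examined within the" auditory, limbic, default-mode and attentional networks. The background in Section 4 also predicts that the attention, default mode and limbic networks will differ from baseline after CPT.

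**The concern.** There are two linked problems.

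First, the plan promises a causal conclusion from the mid-treatment scan and gives no model for it. Without a comparison group, a change seen at mid-treatment fits an effect of CPT, but it also fits time, symptom fluctuation or getting used to the scanner. With no stated contrast, whichever mid-treatment comparison looks interesting could be chosen after the data are seen and then reported as causal.

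Second, the primary imaging outcome and the imaging prediction of Hypothesis 3 are worded as different quantities. Section 6.4.2 speaks of activity *within* networks and ranks none of them. Hypothesis 3 concerns connectivity *between* two named networks. A reader of the results could not tell whether the attention-limbic test is the primary imaging analysis, one of several, or secondary.

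**Working it through.** **1. The plan's own figure.** The enrolment table in Section 6.4.1 adds up: 10 + 18 + 2 = 30, with 18/30 = 60% and 2/30 = 6.7%. The claim that 10 is enough cannot be reproduced. The documents give no effect size, standard deviation, significance level or numeric power for the imaging comparison.

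**2. Where each scan is used.**

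| Scan | Sample-size claim (6.4.1) | Imaging ANOVA (6.4.3) | Other stated use (6.4.3) |
|---|---|---|---|
| Baseline | yes | yes | none |
| Mid-treatment | yes | no | causal inference from temporal change; no model |
| One-month follow-up | yes | yes (the only posttreatment scan scheduled) | none |

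Two other passages mention a mixed model, and neither fills the gap. The model under Hypothesis 3 is for tinnitus-distress and PTSD scores. The missing-data paragraph refers to mixed models in general and sets no imaging time contrast.

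**3. Whether timing can carry a causal claim.** With one intervention level, every participant's scan sequence coincides with the course of CPT. The mean change from baseline to mid-treatment is the sum of any CPT effect, any time effect and any repeat-scan effect. Three scans give two independent changes, and each contains all three components. A third scan describes the shape of the change but does not split it.

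**4. Which quantity is primary.** Read strictly, *within* in Section 6.4.2 points to the wording of Hypothesis 2, and *between* in Hypothesis 3 points to another quantity. The protocol does not keep these words apart. Aim 2 and the primary objective in Section 3 speak of covariance *among* networks, yet Hypothesis 2, which serves Aim 2, speaks of connectivity *within* them. Section 4 speaks of connectivity *between* resting-state networks. Section 6.4.2 can therefore be read either way, and no sentence ranks the attention-limbic test.

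**5. Size, for illustration only.** The documents state no significance level and no multiplicity rule. Assumed: two-sided unadjusted 5% tests, n = 10 (Section 6.4.1), the four networks listed in Section 14.0 item 29, and no true change.

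- *Four within-network tests, none ranked.* If independent, the chance of at least one false positive is 1 − 0.95^4 = 1 − 0.8145 = 0.1855, or 18.5%. Simulated one-sample t tests on change scores (200,000 replicates) with equal correlations of 0.3, 0.5 and 0.7 give about 17.7%, 16.0% and 13.8%.
- *One measure, all three pairwise scan contrasts.* Simulated paired t tests (200,000 replicates) give at least one p < 0.05 in 12.6% and 12.8% (compound symmetry, correlation 0.5 and 0.8) and in 12.4% and 12.2% (first-order autoregressive, 0.5 and 0.8).
- *One named measure and one named contrast.* 5%.

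**The case against.** A reader might infer that the primary imaging outcome does not, or cannot, test Hypothesis 3. The documents do not support that. *Within* may be loose wording for *in*, given how freely the protocol uses *within*, *among* and *between*. The connectivity mapping in Section 6.4.3 rests on the idea that "Inter-connected regions show temporally correlated variations", and with ICA it could yield an attention-limbic measure. Even a strict within-network endpoint would match the prediction in Section 4 that the attention, default mode and limbic networks will be altered. This objection stands: the wording is ambiguous, and the data are able to test the hypothesis.

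A reader might also fear that a change in any network could be passed off as confirming Hypothesis 3. That does not follow. Section 6.4.3 sets each hypothesis above its analysis plan, and Hypothesis 3 fixes the pair, the direction and the time. What remains open is the rank of its test.

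The error rates can be challenged too. The plan never says that four networks will each be tested at 5%, and it does not state three pairwise scan tests. They therefore show what the plan leaves open, not what it prescribes.

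None of this reaches the mid-treatment scan. The causal sentence is explicit, the design has one intervention level, and the stated ANOVA has two time points.

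**Conclusion.** The point holds in two parts of unequal strength.

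The firmer part rests on the text alone. The causal use of the mid-treatment scan is not supported by a design without a comparison group, and the scan is absent from the only stated imaging test although the sample-size statement relies on it.

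The second part is a lack of clarity. Section 6.4.2 and the imaging bullet of Hypothesis 3 are not clearly aligned, and the rank of the attention-limbic test is undeclared. This is not proof of a mismatch, and it does not mean that Hypothesis 3 goes untested.

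Under the assumptions above, the latitude left open amounts to up to an 18.5% false-positive chance across four unranked within-network tests (about 14% to 18% with correlations of 0.7 to 0.3), and about 12% to 13% across three scan contrasts on one measure, against 5% for one named contrast. The plan should be changed, and the change is nearly free. Confidence is medium, because the endpoint part depends on how Section 6.4.2 is read.

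**What to change.** 1. In Section 6.4.3, replace the causal sentence with a statement that mid-treatment results describe the time course of network change and are not evidence of a causal effect of CPT.
2. Analyse all three scans in one repeated-measures mixed model with a subject effect and time as a three-level factor. Make one-month follow-up minus baseline the primary contrast and report mid-treatment contrasts as secondary.
3. Reconcile Section 6.4.2 with Hypothesis 3 in one of two ways:
   - name change in attention-limbic between-network connectivity, baseline to one-month follow-up, as the primary imaging endpoint; or
   - name a specific within-network endpoint and declare the Hypothesis 3 imaging test secondary.

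   In either case, treat the other network measures as secondary.

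The cost is protocol and SAP wording and a little analysis time; no scans or participants are added. The downside is that other network findings become secondary, so a real change outside the named measure would need confirmation elsewhere.

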6. RESEARCH PLAN

6.1 Selection of Subjects

230 **6.1.1. Subject Population.** This study will consent and screen 30 male and female veterans seeking treatment for PTSD to
231 include 10 for analysis. Subjects will be recruited from the San Antonio community.

232 **6.1.2. Source of Research Material.** All measures are being administered for research purposes. For a complete list of
233 measures, see Section 6.2.

234 **6.1.3. Inclusion and Exclusion Criteria.**

235 Inclusion Criteria

- 236
 - 237 • Adult male and female military Veterans (age 18-60) who deployed in support of combat operations post-9/11
238 seeking behavioral health treatment for PTSD and/or tinnitus
 - 239 • Diagnosis of PTSD determined by the Clinician-Administered PTSD Scale - Interview – Version 5 (CAPS-5)
 - 240 • Ability to speak and read English
 - 241 • Meets criteria for tinnitus and considers their tinnitus bothersome, as defined by a score on the Tinnitus Functional
242 Index of 32 or greater

243 Exclusion Criteria

- 244
 - 245 • Currently receiving evidence based treatment for PTSD
 - 246 • Current suicidal ideation severe enough to warrant immediate attention (as determined by the Depressive Symptoms
247 Index- Suicidality Subscale and corroborated by a clinical risk assessment by a credentialed provider
 - 248 • Psychiatric hospitalization in the last 12 months
 - 249 • Current and severe alcohol use warranting immediate intervention based on clinical judgment
 - 250 • Current manic episode or psychotic symptoms requiring immediate stabilization or hospitalization (as determined by
251 the manic and psychosis modules of the MINI)
 - 252 • Evidence of a moderate or severe traumatic brain injury (as determined by the inability to comprehend the baseline
253 screening questionnaires)
 - 254 • Neurobiological disorders
 - 255 • Meniere's disease, temporomandibular joint disorders
 - 256 • History of seizures
 - 257 • History of penetrating head trauma or neurosurgery
 - 258 • Metal objects implanted in the head, ferrous metal filings in the eye
 - 259 • Inflammation of the brain
 - 260 • Cardiac pacemaker
 - 261 • Implanted medical pump or cardiac lines
 - 262 • Heart disease
 - 263 • Currently taking certain types of medication for depression or seizures (tricyclic antidepressants or neuroleptics which
264 lower seizure threshold)

265 **6.1.4. Description of the Recruitment and Prescreening Process.**

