318 participant will be given a copy of the informed consent document (ICD) to read. The research team member obtaining
319 informed consent will then engage the potential participant in an interactive explanation of the study guided by the ICD.
320 After the subject has read the ICD, he or she will be given the opportunity to consider participation and discuss the
321 research with family and friends. The Research Team will be available to answer any questions about the research.
322 Once the potential participant has reached a decision, the advising staff member will review the risks and benefits of study
323 participation and ensure the subject has an understanding of the material discussed, and the risks and benefits of their
324 potential involvement in the study. The advising staff member will have the participant sign the consent form. A copy of
325 the signed ICD will be given to the subject.
326

327 **6.1.6. Subject Screening Procedures.**

328 Following consent, screening and baseline assessment will take place to determine participant eligibility. The entire
329 screening process will take approximately 3 hours. This will include the completion of the questionnaires and interviews
330 outlined in the table in Section 6.2 below. For individuals not meeting study inclusion criteria, the Study Staff will assist
331 coordinating appropriate care outside of the study.
332

333 **6.1.7. Compensation for participation.**

334 Participants will be compensated \$75 for each neuroimaging scan: once prior to enrolling in Cognitive Processing
335 Therapy, once at mid-treatment (after Session 6 and before Session 7), and once at the one-month follow-up after
18-524H, [name], Form BB, 02-28-20, AMD.DOCX
Page 7 of 22

336 receiving Cognitive Processing Therapy. Payment will be provided via a rechargeable MasterCard® ClinCard. The
337 MasterCard® ClinCard is a debit card issued to the study participant. Funds are loaded onto card through the ClinCard
338 website at www.clincard.com. Only authorized users will be able to access the ClinCard website to add funds with a
339 username and password. The ClinCard funds will be available to recipients within 1 business day and can be used as the
340 participant chooses. The participant will be notified that their name, address and date of birth will be shared with a third-
341 party (ClinCard) solely for the purposes of payment processing. This information will only be used for the administration

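### Aim 1 correlates PTSD and tinnitus scores in a sample that entry criteria truncate on both, at an n of 10 set for imaging, and names no analysis set for the baseline scores of those screened out

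*Combined protocol and SAP*

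**What the plan says.** Aim 1 (Section 3) is to find which symptoms PTSD and tinnitus distress share and which are unique to each. The H1 plan in Section 6.4.3 forms symptom clusters from the CAPS-5 and distress domains from the TFI, then states that "Pearson product-moment correlation coefficient analyses will be used to" examine the overlap. It gives no analysis set, target correlation or significance level.

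Section 6.1.3 admits people with a CAPS-5 diagnosis of PTSD and, for tinnitus, a score on the Tinnitus Functional "Index of 32 or greater".

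On numbers, Section 6.1.1 reads "This study will consent and screen 30 male and female veterans seeking treatment for PTSD to" "include 10 for analysis". Section 6.4.1 adds "The recruited sample size will be 30 participants", and the row "Estimate Participant Screen Out" gives 18. Its statement of adequate power for 10 people concerns resting-state networks only.

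Section 6.1.6 states: "Following consent, screening and baseline assessment will take place to determine participant eligibility. The entire" screening visit takes about 3 hours and covers the instruments in the Section 6.2 table, where CAPS-5, PCL-5, TFI and TAQ are all marked at baseline. The battery is therefore scheduled after consent and before eligibility is settled.

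**The concern.** Cutting off the lower end of two positively correlated scales lowers the correlation among those who remain. The entry rules suit the treatment aim but work against the overlap aim. With 10 people the estimate is also very imprecise. Symptoms that do overlap could be reported as unrelated, or called unique to one disorder, because of the cut-offs and the sample size.

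H1 needs neither therapy nor MRI. Someone screened out for an MRI contraindication or a medication can still have usable CAPS-5 and TFI scores, and someone below one threshold carries information on the part of the range that the entry rules remove. Nothing in Section 6.4.3 gives these records a role.

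**Working it through.** **1. The plan's own figure.** Section 6.4.1: 10 required + 18 screened out + 2 withdrawn = 30; 18/30 = 60% and 2/30 = 6.7%. The total reproduces. The 10 cannot be derived for a correlation, because no effect size, alpha or power is given.

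**2. Assumptions, none from the documents.** Bivariate normal severity, underlying r = 0.50, two-sided alpha 0.05, one test. Four CAPS-5 clusters by eight TFI subscales would give 4 × 8 = 32 pairs, so any multiplicity adjustment would lower the power figures below.

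**3. Precision.** Critical r = t/√(t² + n − 2):
- n=10: t = 2.306, r = √(5.318/13.318) = 0.632.
- n=30: t = 2.048, r = √(4.194/32.194) = 0.361.

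The 95% interval around an observed r of 0.50, tanh(atanh r ± 1.96/√(n−3)), is −0.19 to 0.86 at n=10 and 0.17 to 0.73 at n=30.

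**4. Attenuation from selecting on both scales (simulation).**
- Each cut removes 20%, 30% or 40%: r = 0.50 becomes 0.36, 0.33 or 0.30.
- 40% jointly eligible (12/30, all 18 failing on severity): r = 0.29.
- 80% jointly eligible: r = 0.40.

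**5. Power at n=10.** Power = 1 − Φ(1.96 − δ) + Φ(−1.96 − δ), with δ = atanh(r)·√(n−3).
- r = 0.361: δ = 0.378 × 2.646 = 1.000; power 17%.
- r = 0.297: δ = 0.306 × 2.646 = 0.810; power 13%.
- r = 0.24, if selection goes further: δ = 0.245 × 2.646 = 0.648; power 10%.
- r = 0.395, the mildest case: power 20%.

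**6. Power with all 30 depends on what the 30 are.** Here √27 = 5.196.

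| Consented pool | r in pool | Power, n=30 |
|---|---|---|
| r is 0.50 within the pool itself | 0.50 | 81% |
| Pre-screened on both conditions | 0.32 to 0.40 | 41% to 60% |
| High on at least one, cut at 30th percentile | 0.29 | 35% |
| Same, 50th percentile | 0.13 | 11% |
| Same, 70th percentile | −0.05 | 6% |

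For example, r = 0.32 gives δ = 0.332 × 5.196 = 1.72 and power 41%; r = 0.40 gives δ = 0.424 × 5.196 = 2.20 and power 60%. In the last three rows the correlation among people above both cuts is 0.33, 0.27 and 0.22, so pooling gives a lower r than restricting to the eligible.

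**7. Which row fits.** Section 6.1.4 describes a records route that uses earlier CAPS-5 and TFI scores, and a phone screen that reviews the basic entry criteria before consent. That points to the pre-screened row. It does not exclude the last three, because Section 6.1.3 admits people seeking care for either condition or both.

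**The case against.** Four objections carry weight.

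- A reader might infer that the plan discards the screen-outs' data. The text does not say so. H1 names no set and excludes nobody, and the 10 is tied to imaging. What stands is that the Aim 1 population is unspecified and that Section 6.1.1, read as written, limits it to 10.
- A reader might also infer that using all 30 restores the full range and gives 81% power. The recruitment text does not support this: the pool is already selected, and mixing people high on one condition with people high on the other can push r below its value among the eligible.
- H1 is partly meant to help clinicians understand comorbid patients. For that purpose the correlation within comorbid cases is the target, not a biased version of another quantity. This is fair, and it is why the whole pool should not simply replace it as the main estimate. But Aim 1 also asks which symptoms are unique, and that is hard to judge when everyone has both conditions.
- Not every screen-out score is valid. Section 6.1.3 identifies moderate or severe brain injury by inability to comprehend the screening questionnaires, so those scores must be left out. The documents also do not say that the battery is completed once an exclusion appears.

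The abstract's statement that 30 people with both conditions will be enrolled conflicts with Section 6.1.1 and needs reconciling. It would raise n, but the sample would still be selected on both scales.

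**Conclusion.** The point holds in a limited form. The selection variables are the analysis variables, the n of 10 has no stated basis for a correlation, and the plan does not say whose baseline scores enter H1. The downward direction of the truncation effect follows from selecting the upper part of two positively correlated, roughly normal scales. Its size is an assumption, because the documents give no score distributions or expected correlation. The cut acts directly on the TFI, through the diagnosis on the CAPS-5, and only indirectly on the PCL-5 and TAQ.

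At an underlying r of 0.50, power at n=10 is about 10–17%, or 20% under the mildest selection considered. The gain from using all consented participants may be substantial or nil, depending on the make-up of the pool. That supports reporting both populations, with their limits stated.

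**What to change.** - **Section 6.1.1:** limit the 10 for analysis to the imaging and treatment aims, and reconcile the abstract with it.
- **Section 6.4.3, H1:** define the analysis set as every consented participant with a valid baseline CAPS-5 and TFI, leaving out those unable to comprehend the questionnaires.
- **Report two estimates side by side, with confidence intervals:** (a) everyone meeting both the PTSD and TFI criteria, including those screened out for unrelated reasons such as MRI contraindication or medication, labelled as range-restricted; (b) all consented participants with valid scores, labelled as a pre-screened, treatment-seeking pool in which selection can still bias r in either direction relative to the wider population.
- **Interpretation:** do not call a symptom unique on the strength of a null correlation in (a) alone.

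The cost is mainly wording: no added patients, and no added visits where the battery was completed. Section 6.1.4 keeps out of the research data only information on people who do not consent. The downsides are that (b) describes veterans screened for both conditions rather than confirmed comorbid cases, and that some screen-outs may have incomplete batteries, so the number contributing to each estimate should be reported.
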